The sample size for this study is calculated using G-power 3.1.9.7 statistical software to determine the effect size. According to Cohen (1988), effect sizes are categorized as large (0.80), medium (0.50), and small (0.20). Since most research results have an effect size of 0.50, this study sets the criterion of at least a medium effect size. With α =0.05, statistical power (power)=0.80, and effect size set at 0.5, the estimated sample size is 60 individuals. Considering potential changes in the elderly or refusal to participate, a dropout rate of 15% is estimated. Therefore, a total of 70 elderly individuals from community-based activities will be recruited for this study. The inclusion criteria for this study are as follows: (1) aged 65 and above, (2) able to communicate in Mandarin or Taiwanese and willing to complete interviews or self-administered questionnaires, (3) no mobility impairments (e.g., stroke, Parkinson's disease, motor neuron diseases), (4) no severe cardiovascular diseases, (5) no degenerative joint diseases or acute attacks in the past three months, (6) lower limb joint surgery performed more than three months ago, and (7) no dizziness or any unstable health conditions that hinder exercise. During the study period, participants who do not engage in physical

activity for more than three weeks or have missing pre-test or post-test data will be excluded from the statistical analysis.

Ethical Considerations:

Prior to conducting the study, the research proposal will be submitted to the Institutional Review Board (IRB) for review and approval. Approval was obtained from the Taipei Medical University Joint Institutional Review Board (TMU-JIRB) on November 24, 2022, with the approval letter numbered N202210004 (see Appendix 1). This study aims to investigate the effects of VR interactive games as part of exercise prescriptions on the balance function and lower limb strength of elderly participants.

Section 3: Intervention Tools

Hardware Setup:

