The results of ANCOVA analysis (Table 6) revealed that the post-test scores of the experimental group were significantly higher than those of the control group in five assessment outcomes, including the 2-minute step test (p < 0.001), right chair sit and reach (p = 0.010), left chair sit and reach (p = 0.002), psychological quality of life (p = 0.033), and environmental quality of life (p = 0.048). Additionally, the differences in fitness (except for the 30-second chair stand test) and quality of life had effect sizes (partial eta squared) ranging from 0.011 to 0.267, indicating moderate to substantial intervention effects. These results suggest that the intervention in this study was more effective in improving the aforementioned fitness and quality of life compared to regular community activities.

	StatisticsF /(p)	effect size (partial eta
		squared)
BMI	0.195 (0.661)	0.003
30 seconds sit and stand	0.015 (0.904)	0.000
The seat body bends forward (right)	21.154 (<0.001)	0.267
The seat body bends forward (left)	7.091 (0.010)	0.109
Get up and walk Around at 2.4 meters	10.294 (0.002)	0.151
Physiological quality of life	0.667 (0.418)	0.011
Psychological quality of life	0.956 (0.332)	0.016
Quality of social life	4.766 (0.033)	0.076
Environment quality of life	1.405 (0.241)	0.024
The seat body bends forward (right)	4.080 (0.048)	0.066

Table 6Post-test comparison between the experimental group and the

control group

Note: This analysis uses ANCOVA to control the pretest scores and other significant influencing factors

in the pretest. The control variables include: age, education level, and pretest scores of each variable.

Section 3: Analysis and Comparison of Quality of Life Questionnaire

Upon statistical analysis of pre-test and post-test scores (Table 7), it was found that in the experimental group, there was a difference of 0.4points in the physical domain (p = 0.202), no difference in the psychological domain (p = 0.008), a difference of 0.2 points in the social relationships domain (p = 0.500), and no difference in the environmental domain (p = 0.500). In contrast, in the control group, there was a difference of 0.4 points in the physical domain (p = 0.325), no difference in the psychological domain (p = 1.000), and no difference in the social relationships and environmental domains. The results indicate a significant change in the quality of life in the physical domain for the experimental group.

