This study primarily utilized virtual reality interactive games for training. It employed a three-axis inertial sensor to monitor body angle changes during exercise. Older adults wore a waist protector embedded with sensors, which connected via Bluetooth to control a virtual aircraft in the game. Participants moved their bodies forward, backward, left, and right to collide with asteroids and coins in different directions, challenging their balance with varying levels of difficulty such as standing with feet parallel, slightly squatting with feet parallel, and standing with feet apart. implie m itionally, participants were required to raise their hands and perform stretching and bending movements in sync with body movements in the game. This not only increased upper body movement opportunities but also effectively maintained body balance, reducing the risk of falls during

the game. Researchers like Fang et al. (2016) found that using virtual reality Wii Fit games for training for more than 6 weeks can improve dynamic balance ability in older adults.

In this study, a custom-designed virtual airplane game allowed elderly participants in community center activities to effectively train balance and improve flexibility during exercise. By following game instructions for forward and backward movements, participants could earn scores and complete tasks successfully. After 36 sessions, significant improvements were observed in elderly participants who engaged in virtual reality interactive games, particularly in the 2-minute step test (p<0.001) and left and right chair stands (p<0.001, p=0.003). ANCOVA analysis revealed differences in physical fitness (except for the 30-second chair stand) and quality of life, with effect sizes (partial eta squared) ranging from 0.011 to 0.267, indicating moderate to substantial intervention effects. These findings demonstrate that the virtual reality intervention in this study outperformed conventional center-based activities in enhancing physical fitness and quality of life.

Section 3: The impact of virtual reality interactive game intervention on the quality of life of the elderly

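### An effect-size range that starts at 0.011 is called moderate to substantial and leads to an unlimited superiority claim, although three of the eight outcomes it covers have small, non-significant effects

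*Combined protocol and SAP*

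**What the plan says.** The group comparison is an ANCOVA of post-test scores, adjusted for age, education level and pre-test score (Chapter 4, Section 2, item 3, and the note to Table 6). The text first reports that the experimental group's post-test scores were "significantly higher than those of the control group in five assessment outcomes". It names them with their p-values: 2-minute step, right and left chair sit-and-reach, psychological quality of life (QoL) and environmental QoL.

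It then turns to partial eta squared for all fitness measures other than the chair stand and for QoL as a whole, and describes the values as "ranging from 0.011 to 0.267, indicating moderate to substantial intervention effects". It closes by saying that "the intervention in this study was more effective in improving the aforementioned fitness and quality of life compared to regular community activities".

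Chapter 5, Section 2 repeats the range and the label and ends: "These findings demonstrate that the virtual reality intervention in this study outperformed conventional center-based activities in enhancing physical fitness and quality of life".

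The only effect-size benchmark in the document is in Chapter 3, Section 2 (Research Participants), where "effect sizes are categorized as large (0.80), medium (0.50), and small (0.20"). It is given for the sample-size calculation. Chapter 3, Section 6 sets significance at p < 0.05. No benchmark is given for partial eta squared.

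**The concern.** One label is applied to a range whose lower end is close to zero. Table 6 itself shows three outcomes in that range with p-values between 0.24 and 0.42. A reader of the Discussion would take it that every fitness measure other than the chair stand, and every QoL domain, showed at least a moderate advantage for the VR game.

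The three outcomes matter for the trial's question. Its registered title names balance and quality of life. Of the four fitness tests in Chapter 3, Section 5, only the 8-foot up-and-go is described as measuring agility and dynamic balance, and it is the outcome with 0.011. The other two are half of the four QoL domains.

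**Working it through.** **1. Outcomes covered.** Table 6 has ten rows. The text excludes the chair stand (0.000, p=0.904) by name. BMI (0.003, p=0.661) lies below 0.011, so it is outside the range too, although it is not named as an exception. Eight remain: 2-minute step, right and left sit-and-reach, up-and-go, and four QoL domains. If BMI were counted as fitness, the range would start at 0.003 and four of nine outcomes would be non-significant.

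**2. Row identity.** From the third row on, the labels in Table 6 are out of step: the 2-minute step is missing and the right sit-and-reach appears twice. I assign rows by the order of Table 4. The five p-values quoted in the text (<0.001, 0.010, 0.002, 0.033, 0.048) then fall on the right outcomes; for example, the third row, "21.154 (<0.001"), is the 2-minute step. The count of three does not depend on this step, but the outcome names do.

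**3. Reproducing Table 6.** The analysed sample is 30 + 33 = 63. With intercept, group, age, education (as one term) and pre-test score, error df = 63 − 5 = 58. Partial eta squared = F/(F + 58). All ten printed values reproduce to three decimals, and the p-values from F(1, 58) agree to within about 0.001. The arithmetic in the table is sound.

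**4. Conversion to the d scale of Chapter 3, Section 2.** d ≈ 2·√(η²/(1 − η²)), and in reverse η² ≈ d²/(d² + 4):

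- small, d = 0.20: 0.04/4.04 = 0.010
- medium, d = 0.50: 0.25/4.25 = 0.059
- large, d = 0.80: 0.64/4.64 = 0.138

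| Outcome (by row order) | F | F/(F+58) | printed p | d ≈ | size |
|---|---|---|---|---|---|
| Up-and-go | 0.667 | 0.011 | 0.418 | 0.21 | small |
| Physical QoL | 0.956 | 0.016 | 0.332 | 0.26 | small |
| Social QoL | 1.405 | 0.024 | 0.241 | 0.31 | small |
| Environmental QoL | 4.080 | 0.066 | 0.048 | 0.53 | medium |
| Psychological QoL | 4.766 | 0.076 | 0.033 | 0.57 | medium |
| Right sit-and-reach | 7.091 | 0.109 | 0.010 | 0.70 | medium |
| Left sit-and-reach | 10.294 | 0.151 | 0.002 | 0.84 | large |
| 2-minute step | 21.154 | 0.267 | <0.001 | 1.21 | large |

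A cross-check with d = √(F·(1/30 + 1/33)) gives 0.21, 0.25 and 0.30 for the first three. The label therefore fits 0.066 to 0.267, not 0.011 to 0.267.

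**5. Uncertainty.** Approximate 95% intervals for the three small values, from the noncentral F distribution, are 0 to 0.11, 0 to 0.12 and 0 to 0.14. Each includes zero, and each extends past 0.059.

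**6. Why p < 0.05 should not decide the label.** Environmental QoL passes at p=0.048, unadjusted among ten outcomes. Yet Table 7 gives its raw pre-post change as 0.0±0.1 in the VR group and 0.0±0.0 in the control group. Partial eta squared is relative to residual variance after adjustment and has neither direction nor units, so a medium value can sit on a raw change of about zero.

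**The case against.** A reader might infer that the Results text claims superiority on all eight outcomes. The documents do not clearly support that. Item 3 opens by naming the five significant outcomes, Table 6 prints every F, p and effect size, and the closing sentence can be read as pointing back to those five. The abstract's results list only the five. The abstract's conclusion and Chapter 6 limit QoL to the psychological and environmental domains. This narrows the point but does not remove it: the label in item 3 expressly starts at 0.011, the Discussion carries no limit, and the abstract's conclusion and Chapter 6 still claim physical fitness as a whole.

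A reader might also infer that the three results are null, or that the game does nothing for balance. The intervals in step 5 do not exclude a medium effect, so the most that can be said is that no difference was shown. Nor is balance the sole question: the registered title adds quality of life, and the thesis title and objective speak of physical fitness and quality of life.

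Finally, the 0.059 cut-off is a conversion and not a threshold that the document sets. It suits two near-equal groups without covariates, whereas these models are adjusted. That is fair, but the largest of the three values, 0.024, is less than half of 0.059, so modest error in the conversion would not make it moderate. The p-values need no conversion.

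**Conclusion.** The point holds as one of interpretation and reporting. No figure in Table 6 is disputed. Three of the eight outcomes covered (0.011, 0.016 and 0.024; p=0.418, 0.332 and 0.241) are small and non-significant, so the label is wrong for them and the unlimited claim in Chapter 5, Section 2 does not follow from the table. Five of eight (0.066 to 0.267) are medium or large by the same conversion, with p < 0.05.

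This rests on two inferences: the outcome names under the shifted labels, and the approximate conversion from partial eta squared to d. The count of three and the p-values depend on neither. Correcting the text would change what the trial is said to have shown, above all on up-and-go.

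**What to change.** 1. Add adjusted mean differences (VR minus control) with 95% confidence intervals to Table 6, from the same ANCOVA models, and base the interpretation on them. Realign the row labels at the same time.
2. In Chapter 4, Section 2, item 3 and Chapter 5, Section 2, correct the stated range so that the label no longer covers 0.011 to 0.024. Report up-and-go, physical QoL and social QoL, and also BMI and chair stand, as small or negligible and non-significant. Name BMI as left out of the range.
3. Limit the superiority statement in Chapter 5, Section 2, and the general reference to physical fitness in the abstract's conclusion and Chapter 6, to named outcomes with supporting differences. For fitness these are the 2-minute step and right and left sit-and-reach. For QoL they are the psychological domain and the environmental domain, the latter with the caveat that its raw mean change is about zero.
4. State that no difference was shown on up-and-go.

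The cost is wording in four places plus the added estimates from models already fitted. No new data and no change of analysis are needed.

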This study aims to understand the impact of intervention on the functional fitness and quality of life of elderly participants befor and after the intervention. The assessment tools used include functional fitness tests and a quality of life questionnaire, along with the collection of basic participant information. Both groups underwent pre-tests befor the intervention, which included a fall risk assessment, functional fitness assessment, and quality of life satisfaction survey. After completing the 12-week, 36-session intervention, post-tests were conducted to measure the effectiveness of the intervention.

1. Basic Participant Information:

Includes gender, age, exercise habits, self-perceived health status questionnaire, and Body Mass Index (BMI).

2. Functional Fitness Tests:

(a) Chair Stand Test:

Measures lower body strength/endurance.

Participants sit in a chair without armrests and stand up as many times as possible within 30 seconds.

(b) Chair Sit and Reach Test:

Assesses lower body flexibility.

Participants sit on the edge of a chair with one knee bent at 90 degrees and try to reach their toes with their hands. The distance between the fingertips and toes is measured.

(c) 8-Foot Up-and-Go Test:

Evaluates agility and dynamic balance.

Participants sit in a chair, stand up upon hearing a signal, walk around a designated point 8 feet away, and return to the chair. The time taken to complete the task is recorded.

(d) 2-Minute Walk Test:

Measures aerobic endurance.

Participants walk in place for 2 minutes, and the number of times the knees are lifted to a specific height is counted.

3. Quality of Life Questionnaire:

Administered using the "Taiwanese version of the World Health

Organization Quality of Life Questionnaire-Brief Form

(WHOQOL-BREF Taiwanese version)."

Consists of 28 questions divided into four domains: physical health, psychological health, social relationships, and environment.

Each question is scored on a Likert scale ranging from 1 (very poor) to 5 (very good), with higher scores indicating better quality of life. Demonstrates good reliability with Cronbach's α and split-half reliability of 0.92 and 0.93, respectively. Section 6 Data Processing and Statistical Analysis

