less than 30 minutes	0 (0%)	3 (9.1%)	
more than 30 inutes	22 (73.3%)	15 (45.5%)	
30-60 minutes	8 (26.7%)	15 (45.5%)	
Falls experience in the past			1.034 (0.669)
year			
No falls	23 (76.7%)	25 (75.8%)	
≤3 次	6 (20.0%)	5 (15.2%)	
>3 次	1 (3.3%)	3 (9.1%)	

Table 3 Descriptive Statistics

Section 2: Comparison of Functional Fitness

1. Analysis of Demographic Data

Before the intervention of virtual reality interactive gaming, the participants' functional fitness, including height, weight, lower limb muscle endurance, lower limb flexibility, and agility, were assessed descriptively.

In the pre-test assessment, there were no significant differences between the experimental group and the control group in terms of fitness and quality of life, as indicated by independent samples t-tests, as shown in Table 4.

2. Comparison of Pre-test and Post-test within the Experimental and Control Groups

The results of dependent samples t-tests (Table 5) showed statistically significant improvements in four assessment outcomes in the experimental group, including the 2-minute step test (p < 0.001), left and right chair sit and reach (p < 0.001, p = 0.003), and psychological quality of life (p = 0.008).

In the control group, there was a statistically significant improvement in one assessment outcome, the 30-second chair stand test (p = 0.001).

	Test group (N=30)	Control group	t value (p) or
		(N=33)	Z value (p)
pretest assessment			
BMI	27.0 ± 3.5	25.4 ± 3.8	1.77 (0.077) §
30 seconds sit and stand	16.3±4.6	17.7±5.2	-1.19 (0.234) §
2 minutes to step	96.0±20.7	92.5±25.4	0.60 (0.548)
The seat body bends forward (right)	2.9±10.1	2.6±12.0	0.25 (0.799) §
The seat body bends forward (left)	1.2±11.2	1.4±13.4	-0.08 (0.935)‡
Get up and walk Around at 2.4 meters	8.5±3.2	8.4±3.6	0.70 (0.483) §
Physiological quality of life	10.8±1.4	11.4±1.5	-1.75 (0.086)‡
Psychological quality of life	11.1±1.8	11.7±1.8	-1.28 (0.200) §
Quality of social life	11.2±1.9	11.4±1.1	-0.652 (0.515)§
Environment quality of life	10.6±2.2	10.3±2.0	0.090 (0.928) §

Table 4Functional fitness pre-test of the experimental group and the

control group

[‡] Using independent sample t test

§Using the Mann-Whitney U test

Table 5 Intra-group pre- and post-test comparison between the

experimental group and the control group

		Test g	roup (N=30))		Control	group (N=33	3)
			score				score	

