This study initially targeted websites and platforms specifically designed for or targeted at older adults to find digital games recommended on these platforms. Subsequently, games suitable for older adults recommended on non-elderly websites were also collected. Finally, a virtual reality interactive game suitable for use by older adults aged 65 and above in community centers was innovatively created by integrating popular games currently available in the market. The study designed a virtual airplane game, allowing for interactive and group gameplay, enabling four older adults to simultaneously participate in competitive activities. After 36 sessions, significant changes were observed in the experimental group in the 2-minute step test (p < 0.001), left and right chair stands (p < 0.001, p = 0.003), and psychological well-being (p = 0.008). During the exercise, older adults experienced feelings of happiness, excitement, nervousness, and anticipation. However, if the game ended with unsatisfactory scores or due to delays caused by network connectivity issues, feelings of confusion, dissatisfaction, complaints, and low mood emerged. Each gaming session prompted older adults to remember their scores and engage in discussions with others. Through continuous self-challenges in the game, participants not only increased

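### Chapter 5 twice reports the sit-and-reach results as chair-stand gains; the chair stand itself showed no significant gain in the VR arm or between arms

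*Combined protocol and SAP*

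**What the plan says.** Chapter 5, Section 1 counts among the VR arm's significant changes "left and right chair stands (p < 0.001, p = 0.003), and psychological well-being (p = 0.008". Chapter 5, Section 2 repeats this, reporting improvements "particularly in the 2-minute step test (p<0.001) and left and right chair stands (p<0.001, p=0.003".

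The Results text (Chapter 4, Section 2, item 2) gives the same pair of p-values to another test: "left and right chair sit and reach (p < 0.001, p = 0.003), and psychological quality of life (p = 0.008".

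Chapter 3, Section 5 defines the two tests separately. The chair stand is a count of stands in 30 seconds; its stated purpose is "Measures lower body strength/endurance". The sit-and-reach is done with one knee bent and measures the distance between fingertips and toes; its stated purpose is "Assesses lower body flexibility".

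Lower-limb strength is named, with balance, as something the study investigates (Chapter 3, Section 1, and the ethics paragraph of Section 2). Chapter 5, Section 4 says that weekly training of this kind can improve strength.

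**The concern.** A chair stand has no left or right side, and the p-values match the sit-and-reach results exactly, so two Discussion sentences report a flexibility result under the name of a strength and endurance test. Read literally, they credit the VR arm with a significant gain on a test where the trial's own tables show a significant within-arm gain in controls only.

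The chair stand is the only lower-limb strength measure in the fitness battery. The two sentences are therefore the only apparent trial evidence for the strength statement in Section 4. Once the test is named correctly, no reported result on lower-limb strength supports that statement.

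**Working it through.** **1. Where the two p-values come from.** The row labels of Table 5 are displaced from the third row on: the 2-minute step label is missing and the right sit-and-reach label appears twice. Rows can be matched to Table 4 by the VR arm's pre-test values. Table 4 has "The seat body bends forward (right) 2.9±10.1" for the right side and 1.2±11.2 for the left.

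| VR pre-test in Table 5 | Test by Table 4 | Change (pre minus post) | Printed result |
|---|---|---|---|
| 16.3±4.6 | 30-second chair stand | −0.9±3.1 | −56.5 (0.174) |
| 2.9±10.1 | sit-and-reach, right | −4.4±7.4 | −140 (<0.001) |
| 1.2±11.2 | sit-and-reach, left | −4.9±8.1 | −3.29 (0.003) |

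The chair-stand row is not displaced: its pre-test values (16.3±4.6 and 17.7±5.2) agree with Table 4 under the same label.

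**2. Reproducing p=0.003.** Paired t with n=30: t = −4.9/(8.1/√30) = −3.31, p=0.0025 (0.0022 to 0.0029 allowing for rounding of the inputs). The printed t of −3.29 on 29 degrees of freedom gives p=0.0026, which rounds to 0.003. So this p-value belongs to the left sit-and-reach.

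**3. Checking p<0.001.** I read −140 and −56.5 as signed-rank statistics, since neither is possible as a t value with its printed p. (The Table 5 footnote says that the marked rows use Wilcoxon, but the marked left row reproduces as a paired t, so the footnote looks reversed.) With n non-zero differences, z = S/√(n(n+1)(2n+1)/24). For S=−140:
- n=27: z=−3.36, p=0.0008
- n=30: z=−2.88, p=0.004

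The printed p<0.001 is therefore attainable by the normal approximation if at least three differences were zero (two, by the t approximation to S). A paired t on the same row gives −4.4/(7.4/√30) = −3.26, p=0.003. The right side is significant on any of these.

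**4. The chair stand itself.**
- VR arm, 16.3 to 17.1: S=−56.5 gives p=0.175 at 27 non-zero differences, in line with the printed 0.174. A paired t gives −0.9/(3.1/√30) = −1.59, p=0.12.
- Control arm, 17.7 to 18.5, change −0.8±1.5: printed p=0.001. A paired t gives −0.8/(1.5/√33) = −3.06, p=0.004.
- Between arms, Table 6: F=0.015 on 1 and 58 degrees of freedom gives p=0.903 (printed 0.904, a rounding difference). Partial eta squared = 0.015/(0.015+58) = 0.0003, printed as 0.000. I inferred the 58: it reproduces the printed partial eta squared of 0.109 for F=7.091 and 0.151 for F=10.294.

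The mean gains are nearly equal, 0.9 and 0.8 repetitions. Only the control gain is significant, and its changes vary less (SD 1.5 against 3.1).

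**5. Left and right.** The Results text and both Discussion sentences name left first and give p<0.001 first. By step 1 the order should be right p<0.001, left p=0.003. The ANCOVA text (right p=0.010, left p=0.002) follows the realigned row order and confirms the matching.

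**The case against.** The strongest reply is that this is a wording slip, plausibly from translation, with its own correction nearby. In Chapter 5, Section 2 the next sentence excepts the 30-second chair stand from the ANCOVA differences, and an earlier sentence speaks of balance and flexibility. Neither faulty sentence uses the word strength, and the mention of two sides signals an error. The abstract and Results text name the sit-and-reach, and the conclusion claims no chair-stand benefit. The stated objective and hypothesis are physical fitness and quality of life, not strength as such.

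Much of this stands, and it limits the reach of the error. A reader might infer that the trial's headline claims rest on a false strength result; they do not. But the exception in Section 2 concerns the between-arm comparison, while the faulty sentence concerns change within the VR arm. It therefore leaves two adjacent sentences in apparent conflict and does not correct the first. Section 1 has no caveat at all.

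A reader might also infer that the Discussion independently swapped the two sides. The documents do not support that. The order is already in the Results text, and on Table 5's printed labels the left row does carry p<0.001. The reversal appears only after the labels are realigned, and it assumes that the p-values follow the order in which the sides are named, since the text does not say so expressly.

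**Conclusion.** The point holds as a misreported result in two Discussion sentences. The p-values <0.001 and 0.003 are sit-and-reach results. The chair stand was not significant within the VR arm (p=0.174) or between arms (p=0.904), and rose significantly only in controls (p=0.001). The statement in Chapter 5, Section 4 that training can improve strength has no support from the trial's only lower-limb strength test.

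A reader might go further and conclude that the trial showed VR has no effect on strength. That does not follow: p=0.904 in 63 analysed participants means that no significant difference was shown, not that none exists.

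The mislabelling is certain from the test definitions and the matching p-values, and does not depend on realigning Table 5. The left/right order does depend on it and is secondary: both sides are significant either way. No design feature, analysis or tabulated estimate is affected.

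**What to change.** - In Chapter 5, Sections 1 and 2, replace chair stands with chair sit-and-reach.
- Add a sentence to Chapter 5: the 30-second chair stand showed no significant change within the VR arm (p=0.174) and no significant difference between arms (p=0.904), which does not establish absence of an effect.
- In Chapter 5, Section 4, remove the strength claim or qualify it to say that this trial's strength test does not support it.
- Check both sit-and-reach p-values and their sides against the source data. Then correct the row labels of Tables 5 and 6 and the left/right order in Chapter 4, Section 2 and Chapter 5, Sections 1 and 2 in one step. Changing the text alone would make it disagree with the printed left row of Table 5. Check the Table 5 footnote at the same time.

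The cost is text and label correction plus one look at the source output; no new analysis is needed. One apparent benefit of the VR programme is withdrawn.
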